This **intervention pilot feasibility study** will assess the impact of auricular acupressure as an additional non-pharmacologic therapy for infants at risk for developing iatrogenic Withdrawal Syndrome (IWS) in the Pediatric Cardiac Intensive Care Unit (PCICU) of Monroe Carell Jr Children's Hospital at Vanderbilt (MCJCHV). We will recruit **40 healthy, 34 weeks gestational age or older infants** exposed to prolonged medications (greater than 5 days) for cardiac procedures that may cause withdrawal upon cessation such as opioids, benzodiazepines, or other sedative medications. Participants will receive the auricular acupressure in addition to the standard of care such as clustered nursing care, touch, position change, environmental controls, holding, and swaddling. Within 24 hours of implementing a weaning protocol, acupressure will be applied to three designated points of one ear following the NADA protocol acupuncture technique while also incorporating the Near-Term Infant (NTI) conceptual framework identified elements (see figure 3). Acupressure will be administered via stickers that are adhesive to the skin like a Band-Aid (see figure 1). These stickers include a vaccaria plant seed in the center that applies continuous light pressure on the designated points. This form of acupressure was selected as it is organic and does not contain metal which may interfere with emergency medical care such as imaging. After the initial 24 hours of application, stickers will be removed, the infant's skin will be assessed for any disruption such as bruising or discoloration, and the stickers will be rotated to the infant's other ear at the same NADA protocol auricular sites. Acupressure stickers will be removed and applied to the opposite ear every 48-72 hours until withdrawal symptoms improve (1). Withdrawal symptoms are measured every 6 hours with the enhanced Withdrawal Assessment tool (WAT) as part of the standard of care. Upon completion of the weaning regimen, infants with a score of less than or equal to 3 or less than 2 above baseline with no more than 2 rescue medication doses in 24 hours will have the acupressure removed.

Figure 1: Auricular Acupressure to NADA Protocol Sites

Acupressure Sticker	Auricular Application	NADA Protocol Points: Shen Men, Liver, Lung
		 
Key: ● - Hidden Points

1.0 Background

Opioid and benzodiazepine medications are necessitated in the treatment of critically ill infants in the cardiac intensive care unit to provide pain relief and anxiolysis. However, use of these modalities are associated with a multitude of uncomfortable symptoms surrounding physical dependence and may lead to withdrawal syndrome, bowel dysfunction, as well as exacerbation of delirium (2). Additionally, long term use of opioids and benzodiazepines in the infant population may impair neurodevelopment (3-5). This is especially concerning for infants undergoing cardiopulmonary bypass as this intervention further places this population at risk for impaired neurological development (6). These medications further contribute to prolonged hospital stays as they must be gradually weaned (7, 8).

Given the sequelae of the prolonged opioid and benzodiazepine exposure in this vulnerable population, first line treatments involve the maximization of non-pharmacologic therapies. These treatments include swaddling, reduction in environmental stimulation, use of sound machines or music, vibration, and soothing touch (9, 10). Yet, these treatments are not always successful in significantly reducing symptoms of withdrawal (with significance referring to reductions that do not require additional medication administrations).

The NADA protocol uses an auricular acupuncture technique created by a physician for the treatment of addiction and has demonstrated efficacy in the adult population (11-13). Acupuncture and acupressure studies in pediatric populations have also demonstrated improvement in multiple symptoms commonly experienced by infants in withdrawal. These symptoms include pain, agitation, crying, feeding difficulties with subsequent growth impairment, and sleep disturbance (14-25). Current evidence suggests acupuncture and acupressure are safe on neonates, but high quality randomized controlled trials are needed to confirm efficacy for the treatment of withdrawal (1, 23-28). This study, with the use of the NTI, will establish efficacy and provide a framework to guide future acupuncture and acupressure studies.

2.0 Rationale and Specific Aims

Sedative medications such as opioids and benzodiazepines are commonly administered to improve comfort of infants undergoing cardiac surgical procedures. Unfortunately cessation of these medications are commonly associated with onset of uncomfortable withdrawal as infants become physically dependent on these medications (29, 30). This condition is known as Iatrogenic Withdrawal Syndrome (IWS) and is further associated with impaired neurological development as well as prolonged mechanical ventilation and hospital stays (3-5, 31-33).

Infants with IWS experience a multitude of symptoms shared by other infant conditions that have been improved with acupuncture including tremors, hypertonicity, agitation, disrupted sleep, feeding difficulty, vomiting, diarrhea, temperature instability, tachypnea, and impaired weight gain (34-37). Treatments focus on non-pharmacologic adjuncts that support physiologic stability and prevent further developmental difficulties, prolonged hospital stays, and interrupted maternal bonding (9, 38, 39). These therapies include swaddling, position change, soothing touch, and environmental controls; however, *they have not traditionally included acupressure as a non-pharmacologic adjunct*. Although standard interventions are helpful, there remains a need to optimize these interventions and further reduce or prevent the use of medication.

Current evidence suggests that acupuncture is safe and beneficial for multiple conditions that impact neonatal and pediatric populations including withdrawal, yet this therapy remains underutilized as there is a lack of high-quality studies evaluating feasibility and therapeutic efficacy in the treatment of dependence (1, 10-24). A less invasive acupuncture therapy is acupressure, a technique that applies mild pressure via stickers, similar to Band-Aids, to designated body points rather than needle insertion to provide a therapeutic benefit.

Acupressure may serve as an additional *non-pharmacological adjunct to ease the severe discomfort of withdrawal in infants physically dependent on medications*.

In addition to therapeutic utility of acupressure, it may be cost effective by decreasing hospital stays and the need for more expensive and invasive pharmacologic interventions (9). **In this pilot feasibility study, acupressure will be used as an additional intervention to current, standard therapies.** The Near-Term Infant conceptual framework (NTI) guided the creation of our acupressure protocol to ensure incorporation of standard of care as well as optimization of acupressure elements to produce healthy outcomes in infants at risk for developing iatrogenic withdrawal syndrome. This acupressure protocol has been implemented at MCJCHV in the neonatal abstinence syndrome (NAS) population and was deemed feasible, accepted by healthcare providers and mothers, as well as safe. If proven feasible and beneficial within a PCICU population, further studies may be conducted to evaluate the efficacy of acupressure in easing with withdrawal symptoms as measured by the enhanced withdrawal assessment tool (WAT-1), when applied in conjunction with standard treatments.

Aim 1: Assess feasibility of delivering an acupressure protocol for the treatment of withdrawal in a pediatric cardiac intensive care unit. Feasibility will be assessed with successful completion of the following objectives:

- a. Achieve recruitment and consent of 4 parents per month whose infant has been exposed to opioids and/or benzodiazepines for greater than 5 days, with a retention of 80% or higher during a 24 month time period (n=40).
- b. Deliver the acupressure protocol to 20 infants at risk for developing withdrawal within the standard of care as an additional non-pharmacologic intervention (20 infants will receive standard of care).

Aim 2: Assess impact of auricular acupressure on withdrawal symptoms for an infant physically dependent on opioid and/or benzodiazepine medications. Efficacy of auricular acupressure will be assessed, in line with the standard of care, with comparison of the following assessments among intervention and control groups:

- a. Duration of opioid and/or benzodiazepine exposure
- b. Duration of wean phase
- c. Duration of mechanical ventilation
- d. Total medication dosage as measured in morphine equivalents and benzodiazepine dosages (mg/kg/patient)
- e. Hospital length of stay
- f. Severity of withdrawal symptoms as measured by the Enhanced Withdrawal Assessment Tool (WAT-1)
- g. Presence and/or severity of delirium as measured by the Pediatric Confusion Assessment Method for the Intensive Care Unit (psCAM-ICU)
- h. Severity of agitation as measured by the Richmond Agitation Sedation Scale (RASS)
- i. Infant Pain scores as measured by Faces, Leg, Activity, Cry, Consolability Scale (FLACC)

Aim 3: Assess acceptability and implementation of the acupressure protocol as an adjunct treatment for withdrawal syndrome within the standard of care.

- a. Examine parental satisfaction of acupressure as an additional treatment as measured by the Client Satisfaction Questionnaire (CSQ8).
- b. Assess provider and staff satisfaction of acupressure as an additional therapy as measured by Acceptability of Intervention Measure (AIM), Intervention Appropriateness Measure (IAM), and Feasibility of Intervention Measure (FIM).
- c. Assess qualitative feedback as reported by parents and healthcare providers.

Impact: Results from this proposed study may expand first line, non-pharmacological therapy for infants experiencing withdrawal symptoms. Offering enhanced care for IWS infants while reducing costs related to hospital treatments is a public health concern during an opioid epidemic. Acupressure is safe, noninvasive, inexpensive, and efficiently implemented for

disorders with similar conditions to withdrawal syndrome, thus warranting additional investigation for consideration as an included standard of practice for post procedural infants.

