4.0 Inclusion/Exclusion Criteria

This prospective pilot study will be conducted over a 24-month period and will enroll a total of 40 infants. Infants will be randomized in a 1:1 ratio to the two groups; randomization will occur within REDCap. Inclusion criteria are as follows: infants, 34 weeks or greater gestation, exposure to opioids and/or benzodiazepine medications for 5 days or more, beginning a stable wean, and maternal age of 18 or older as these individuals are able to consent for themselves (see Table 2). Exclusion criteria will be captured in the medical record as follows: hemodynamic instability, transfer to another facility prior to completion of the weaning regimen or death. Parents identified by health care providers in the PCICU will be approached by study providers ([name], [name], [name], [name], or [name]) in the PCICU. Project procedures will be described and if participants would like to enroll in the study, the consent process will be completed by study providers. Following informed consent, acupressure will be administered within 24 hours MCJCHV. Healthcare providers caring for these infants will be identified through the medical record and subsequent surveys sent through their VUMC email. No ethnic group will be targeted or excluded from this study.

Table 2: Inclusion and Exclusion Criteria

Inclusion	Exclusion
34 weeks gestational age to 1 year of age	Transfer to another facility prior to wean completion
Maternal age 18 or older	Re-escalation of care/Worsening Illness
English speaking	Death
Hemodynamically stable	

Exposure to opioid and/or benzodiazepine for 5 days or more	
---	--

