10.0 Statistical Considerations: Analysis Plan

The study sample will be characterized using descriptive statistics including mean/median, standard deviations/interquartile range, proportions and percentages as outlined below. Benchmarks for success are summarized in Table 2.

Data Analysis Aim 1. The primary goal of this aim is to assess feasibility and implementation of this study including recruitment, retention, and execution of and adherence to the acupressure protocol. Feasibility measures will be reported as frequencies and proportions (% of eligible patients enrolled, % of patients prematurely terminating treatment, % of patients completing all study assessments, % of data collection procedures completed, % of missing medical record data). Feasibility will be determined through the following benchmarks: a) recruitment success: recruitment rate of 2 infants per month over the proposed 24-month time frame (80% of 40 (ex 32) enrolled); b) study retention: retention of >80% of participants through all assessment periods, c) adherence to the acupressure administration protocol: advanced practice providers will record at least 90% of all acupressure sessions in the REDCap database and medical record.

Data Analysis Aim 2. Descriptive data will be generated for the outcomes detailed in Table 2: Aim 2 by treatment group. Given the feasibility goal of this study, we will not conduct formal statistical tests of association between the two treatment groups, but we will provide descriptives by groups and measures of variability. These statistics will inform us of data trends. Descriptives will be generated based on the intent to treat principle.

Data Analysis Aim 3. Parental satisfaction with acupressure as an additional non-pharmacologic intervention will be reported as means with standard deviations and percentiles of the CSQ8 scores within each category of the following: excellent, good, fair and poor. Provider and staff acceptability of acupressure as an additional non-pharmacologic treatment will be measured with the Acceptability of Intervention Measure (AIM), Intervention Appropriateness Measure (IAM), and Feasibility of Intervention Measure (FIM). These measures will be reported as frequency distributions and proportions (% of AIM scores, % of IAM scores, and % of FIM scores).

Table 2: Assessment Measures

Outcomes	Measures	Time Point

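### Aim 1b requires 20 infants on acupressure, but Section 10 counts 32 enrolled as recruitment success, which at 1:1 gives about 16

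*Combined protocol and SAP*

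**What the plan says.** Section 2.0 introduces the Aim 1 objectives with "Feasibility will be assessed with successful completion of the following objectives". Objective b is to "Deliver the acupressure protocol to 20 infants at risk for developing withdrawal within the standard of care", and a parenthesis adds that "20 infants will receive standard of care".

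Section 4.0 gives the planned size and allocation: "This prospective pilot study will be conducted over a 24-month period and will enroll a total of 40 infants", and "Infants will be randomized in a 1:1 ratio to the two groups; randomization will occur within REDCap". It does not mention blocking or stratification.

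Section 10.0 (Data Analysis Aim 1) says that three benchmarks decide feasibility. The recruitment benchmark is a rate of 2 infants per month for 24 months, followed by the gloss "80% of 40 (ex 32) enrolled". The other two are retention above 80% and the recording of at least 90% of acupressure sessions. None of the three counts infants who received acupressure.

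The opening summary says "Participants will receive the auricular acupressure in addition to the standard of care" and mentions neither randomisation nor a control group. A sentence in Section 4.0 likewise places acupressure within 24 hours of consent without limiting it to one arm.

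**The concern.** Both Section 2.0 and Section 10.0 present themselves as the rule by which feasibility is judged. Section 2.0 asks for a fixed number of infants treated. Section 10.0 accepts enrolment at 80% of plan, and 1:1 allocation carries that shortfall into the acupressure arm. Aim 1b was not lowered to match.

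Feasibility is the main purpose of this pilot, and no formal between-group tests are planned, so the feasibility verdict is its principal conclusion. If enrolment ends in the 30s, which Section 10.0 explicitly tolerates, the investigators could report success under Section 10.0 or an unmet objective under Section 2.0 from the same data. Leaving that choice until enrolment is known weakens the conclusion either way.

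**Working it through.** **Inputs.** Planned enrolment N = 40 and 1:1 allocation (Section 4.0). Delivery target of 20 (Aim 1b). Recruitment benchmark of 2 per month for 24 months, glossed as 80% of 40 (Section 10.0).

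**Reproducing the plan's own figures.**
- Planned arm size: 40 × 1/2 = 20. This agrees with Aim 1b.
- Enrolment floor: 0.80 × 40 = 32. This agrees with Section 10.0.
- Benchmark rate: 2 × 24 = 48. This matches neither 32 nor 40. Reaching 32 in 24 months needs 32/24 = 1.33 per month, and reaching 40 needs 40/24 = 1.67 per month.

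**Acupressure arm at the enrolment floor.** 32 × 1/2 = 16, and 20 − 16 = 4 short (4/20 = 20%).

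**Totals at which the two rules disagree, under balanced allocation.** Aim 1b needs N/2 ≥ 20, so N ≥ 40. At N = 38 the arm is 19. At N = 39 it is 19 or 20, depending on which arm takes the odd infant. So every N from 32 to 38 passes the 32-infant benchmark and fails Aim 1b, and 39 may do either.

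**If allocation is not balanced.** The method is not stated. Assuming simple randomisation, the acupressure arm X follows Binomial(N, 0.5), and P(X ≥ 20) is:

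| N enrolled | Expected arm | P(X ≥ 20) |
|---|---|---|
| 32 | 16 | 0.108 |
| 34 | 17 | 0.196 |
| 36 | 18 | 0.309 |
| 38 | 19 | 0.436 |
| 40 | 20 | 0.563 |
| 48 | 24 | 0.903 |

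At 32 enrolled, Aim 1b is therefore missed with certainty under balanced allocation, and with probability 1 − 0.108 = 0.892 under simple randomisation.

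**On the rate reading of the benchmark.** At 48 enrolled a balanced arm is 24. If enrolment is capped at the planned 40, it is 20. Aim 1b can be met in both cases.

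**The case against.** The strongest defence is that nothing is miscalculated. A plan of 40 (20 per arm) beside a success floor of 80% of plan is an ordinary pairing of target and threshold. Aim 1b, with its parenthesis about the 20 controls, can be read as describing planned arm sizes, and Section 10.0 as the decision rule. On that reading nothing fails at 32. The defence also notes that the conflict uses only one half of a benchmark that contradicts itself, since the rate half leads to 48.

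Part of this stands. The 20 is sound as a planned arm size, and 16 is derived from a minimum, not a rival plan. But Section 2.0 makes completion of the objectives the test of feasibility and does not present 20 as a planning figure. The rate reading does not remove the conflict either, because 32 is the only enrolled count that Section 10.0 names as success. The unclear benchmark makes the problem worse.

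Two stronger readings should be resisted.
- A reader might infer that the documents give three competing counts of treated infants: everyone, 20 and 16. They state only one, 20. Nowhere do they say that all participants receive acupressure, and Sections 2.0, 4.0, 6.1 and 10.0 make the two-group design clear. The summary sentence is loose drafting and plays no part in the shortfall at 32.
- A reader might infer that, even at 40 enrolled, Aim 1b is nearly unattainable because no infant in the arm may fail to complete. The documents do not support this. They do not define delivery as a completed course, acupressure has no fixed length, and no completion rate is given. The retention benchmark covers assessments in both groups, which is a different quantity.

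**Conclusion.** The plan is wrong as written, in a limited way: two success criteria for the same aim are incompatible over a range of enrolment that the plan itself calls successful. At the 32-infant floor the acupressure arm is about 16 against a required 20. Under balanced allocation, totals from 32 to 38 satisfy Section 10.0 and fail Aim 1b.

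This rests on taking Section 2.0 at its word that objective b is a condition of feasibility, and on reading the recruitment benchmark by its stated count of 32. If the rate of 2 per month is what was meant, the conflict can disappear, but then the 32 is wrong and the benchmark still needs correcting. The certainty of the shortfall assumes balanced allocation; under simple randomisation it is about 89% at 32.

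The planned sample size, the allocation and the Aim 2 descriptive summaries are unaffected.

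**What to change.** 1. State one enrolment benchmark in Section 10.0, as a count or as a rate that reproduces that count over 24 months.
2. Restate Aim 1b to agree with it, in one of two ways:
   - as a prespecified proportion of infants randomised to acupressure, with 20 kept as the planned arm size. The documents supply no threshold, so the investigators must choose one. If it were 80%, for illustration, this would be 13 of 16 (0.8 × 16 = 12.8, rounded up) or 16 of 20; or
   - as a count matched to the enrolment floor, which is 16 if 32 is kept.

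   The proportion is the more robust choice, because without blocked allocation a fixed count can be missed through chance imbalance alone.
3. Say what counts as delivery for an individual infant, and list the same criterion in Section 10.0, which at present has no benchmark for infants treated.
4. As a wording correction only, limit the summary sentence "Participants will receive the auricular acupressure in addition to the standard of care" and the Section 4.0 sentence on acupressure after consent to infants randomised to the intervention arm.

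The cost is edits to the summary and Sections 2.0, 4.0 and 10.0, best made before enrolment totals are known. No patients or data collection are added.

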3.0 Animal Studies and Previous Human Studies

There is a multitude of research, which has demonstrated efficacy and safety of acupuncture and acupressure in the neonatal and pediatric population; including research within MCJCHV by the PI yielding no adverse outcomes (28). This treatment has also exhibited therapeutic results in veterinary medicine (40). In pediatrics, acupuncture has demonstrated improved myofascial pain and postoperative nausea/vomiting (41, 42). For infants, acupuncture and acupressure has reduced crying in infants with colic and reduced pain during procedures (14, 19, 22, 43). Incidentally, these positive effects can lead to better attachment with mothers. Several studies have outlined the presence of active ear points in the neonate which propose the use of auricular acupuncture or acupressure should be considered as an adjunct treatment (44-47). More specific research studies in NAS reveal acupuncture and acupressure are practical non-pharmacologic interventions (1, 9). Laser acupuncture has been performed on infants with NAS and resulted in reduction in morphine use, diarrhea, length of stay and improved feeding as well as sleep (23-25). Acupressure in combination with massage has also demonstrated efficacy in premature infants weight gain (21). Acupressure is the least invasive technique and very well tolerated (48). A similar study performed acupressure on NAS infants in 1992-1996 with several limitations but there were no adverse reactions or skin disruption noted (1). In this study, ear seeds were left in place for up to 72 hours, following the NADA protocol without any negative effects. Limitations included lack of control for additional acupressure applied by mothers, lack of blinding (sham), and timely application of the seeds (within 24 hours of birth).

